1.4 Study Design

This study is a double-blind, placebo-controlled, two-arm trial in which 120 binge drinkers with AUD will be randomly assigned to receive 12 weeks of kudzu or placebo, to be taken on an as-needed basis (see Figure 2) with 1- and 3-month post-treatment follow-up visits. This efficacy study will enroll sexually active, binge drinkers with AUD because they are the most likely population to benefit from this intervention by limiting harms associated with heavy alcohol use and decreasing alcohol-related sexual risk behaviors. A study clinician will perform the Structured Clinical Interview for the DSM-V (SCID) to screen for AUD and determine eligibility. Upon enrollment, 120 participants will be randomized 1:1 to kudzu extract (2 grams) or placebo for targeted administration. Participants will be seen weekly for behavioral surveys, urinalyses, study drug dispensing, and alcohol use counseling. Safety laboratory assessment, vital signs, and the audio computer assisted survey instrument (ACASI) will be completed monthly. Efficacy, tolerability, and acceptability (Specific Aims 1-4) will be assessed upon trial completion as measured by number of binge drinking occasions and numbers of drinks on drinking days via timeline follow-back at weekly visits; number of EtG-positive urine samples; sexual risk behavior data through monthly surveys via ACASI; frequency of adverse events; and cumulative medication adherence data at week 12. Durability of intervention effects will be evaluated at 1- and 3-month post-treatment visits.

1.4.a. Study Participants, recruitment, and inclusion/exclusion criteria. We will recruit a total of 120 racially/ethnically diverse sexually active, binge drinkers with AUD will be enrolled in the study. Subjects will be San Francisco Bay Area residents between 18-70 years of age. The project is designed specifically for binge-drinkers at high risk for HIV transmission or acquisition.

1.4.b. Recruitment.

For this study, we will combine several strategies that have proven successful in our previous studies with alcohol- and substance-using individuals:

Advertisements: We will run advertisements in the local papers catering to the community and widely read by our participants.

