We are currently implementing the Interim UCSF Policy on Human Subjects-Related Research visits during the COVID-19 outbreak. The A-Hack study is considered essential research. We have stopped screening and enrollment visits until the shelter-in-place order is lifted. The weekly and post-treatment visits are being conducted remotely according to the interim policy guidelines. We have given the active participants up to 6 weeks of study medication during the shelter-in-place order. The monthly visits (M1, M2 and M3) include safety labs to ensure that participants do not have any adverse events to study medication. We are proposing that these in-clinic visits are conducted at weeks 6 and 12 instead of monthly for the safety of our participants during the shelter-in-place order. We will evaluate the interim policy each two weeks or when necessary according to UCSF IRB guidelines.

1.5.a. Prescreening.

Potential participants will be asked brief eligibility screening questions in person or over the phone after providing verbal consent.

1.5.b. Consent.

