Surrogate measures for hypothesized kudzu mechanisms		
Alcohol physiological effects, mood states and risk behaviors during drinking sessions ¹⁵⁷	ACASI	W
Alcohol subjective effects scale (SES) on intensity of intoxication and of impairment ; Length of subjective effects of first alcohol drink; ¹⁵⁸ Desire for alcohol ¹⁶⁸	ACASI	W
Binge-drinking score from Alcohol Use Questionnaire; ^{159,160} Speed of drinking/drinking rate; ¹⁶¹ Latency/time delay between first and second drink during drinking sessions ¹⁶¹	ACASI	W
Biphasic alcohol effects scale (BAES) for subjective nature of intoxication (stimulation and sedation) ¹⁶²	ACASI	W
Trial process measures		
No. pre-screened, screened, enrolled; visits attended, overall retention; participant satisfaction with trial	Visit database, ACASI	Ongoing M 3
Additional covariates		
Demographics (e.g., age, race, education)	ACASI	E
Alcohol Use Disorders Identification Test (AUDIT) ¹⁶³	ACASI	E, M
Center for Epidemiologic Studies Depression Scale ¹⁶⁴	ACASI	E, M
Brief Symptom Inventory ¹⁶⁵	ACASI	E, M
Severity of Dependence Scale ¹⁶⁶	ACASI	E, M
Visual Analog Scale Craving Scores ¹⁶⁷	ACASI	E, W

Notes: E=Enrollment; M=Monthly; W=Weekly; D=Daily PT=Post-Treatment

than monthly until the shelter-in-place order is lifted. This is for the safety of our participants.

Medications taken 30 days prior to enrollment and while enrolled in the study will be documented on a concomitant medications form.

1.1.b. Potential Risks.

Adverse drug effects: A primary risk of participation in this study is the potential of AEs due to taking kudzu. As part of the informed consent process, participants will be informed of the potential risks of taking kudzu. As an edible plant, the roots, flowers and leaves of kudzu has long been used for a wide range of food recipes and consumed as tea in East Asia.⁶³ Hence, kudzu is believed to be extremely safe for human consumption.

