We will use generalized estimating equations (GEE) to estimate treatment effects on repeated study outcomes. Primary analyses will be by intention-to-treat, without regard to adherence to treatment. In our prior trials, we had excellent retention and visit adherence. Nonetheless, in this high risk population, missing data may be encountered.^{175,176} We will conduct sensitivity analyses imputing all missing urine samples as positive, adjusting for baseline correlates of missingness, and using inverse probability of censoring weights.¹⁷⁷

Aim 1: To determine the efficacy of targeted kudzu versus placebo in reducing binge drinking among sexually active binge drinkers with AUD, as determined by number of binge drinking days in timeline follow-back (TLFB), by treatment arm. GEE Poisson models with robust standard

errors will be used to assess reductions on weekly drinking outcomes. Baseline TLFB results will be included in the analysis. Minimum detectable effects (MDEs): Based on the prior Project iN trial (93% retention), we conservatively estimate that 80% of participants will be retained at 12 weeks. Using estimates based on Project ECHO for the within-subject correlation and over-dispersion of the outcomes, as well as the mean frequency among controls, we estimate that this study will have 80% power in 2-sided tests with a type-I error rate of 5% to detect 28% reductions in numbers of binge drinking occasions, as well as 11% reductions in the average number of drinks on drinking days. In exploratory analyses, we will evaluate the durability of intervention effects on drinking outcomes at 1- and 3-month post-treatment visits.

Aim 2: *To determine the efficacy of targeted kudzu versus placebo in reducing alcohol consumption among non-dependent individuals with AUD*, as determined by the proportion of ethyl glucuronide (EtG) positive urines, by treatment arm. GEE logistic models with robust standard errors will be used to assess reductions frequency of positive urine tests, accounting for within-subject correlation. MDEs: Using the assumptions for retention for Aim 1, as well as estimates based on biomarker data from [name] et al.'s study on topiramate for alcohol use disorders¹⁷⁴ for the within-subject correlation and control group urine positivity rate, we estimate that the study will have 80% power in 2-sided tests with a type-I error rate of 5% to detect 15-24% reductions in the urine positivity rate in the treatment arm.

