Aim 3: *To determine the efficacy of targeted kudzu versus placebo in reducing alcohol-associated sexual risk behaviors and incidence of STIs*, by treatment arm, we will use GEE Poisson models with robust standard errors for the four monthly ACASI assessments on numbers of sex partners, HIV-serodiscordant condomless sex partners, condomless sex partners while intoxicated with alcohol, and condomless sex events with serodiscordant partners, including the baseline value. In the event that these outcomes are severely over-dispersed, we will analyze indicators for any self-report of each behavior, using GEE logistic models. We will use GEE logistic regression models to evaluate differences in incidence of STIs between kudzu and placebo arms over time. Incidence will be evaluated as a composite outcome (i.e., any incident STIs), as well as by type (i.e., incident syphilis, gonorrhea, or Chlamydia), and, for gonorrhea and Chlamydia, by site (i.e., urethral, oral, vaginal, or rectal). MDEs: Based on estimates of within-subject correlation and control prevalence from our Project Echo trial, we estimate that the study will have 80% power to detect 32% reductions in numbers of male anal sex partners, 59% reductions in serodiscordant condomless anal sex partners, 48% reductions in condomless anal sex partners while intoxicated with alcohol, and 58% reductions in condomless anal sex events with serodiscordant partners in the treatment arm. In analyses using GEE logistic models, we will have 80% power to detect reductions of 15% for any male anal sex partners, 39% for any HIV-serodiscordant condomless anal sex partners, 40% for any condomless anal sex partners while intoxicated with alcohol, and 31% for any condomless anal sex events with serodiscordant partners in the treatment arm. After accounting for expected loss to follow-up, we will have an estimated 80% power in 2-sided tests with a type-I error rate of 5% to detect reductions of 23-26 percentage points in the incidence of STIs at month 3, depending on the control rates, assumed to be in the range 30-40%, and within-subject correlation of these outcomes, assumed to be 0.1 to 0.3; both inputs were based on data in an ongoing PrEP demonstration project.

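### Aim 3 most naturally counts the enrolment survey as one of four outcome records and names no post-baseline contrast; a single arm term over all four would shrink the estimated effect by about a quarter

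*Combined protocol and SAP*

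**What the plan says.** Section 1.7 opens with a general statement: "We will use generalized estimating equations (GEE) to estimate treatment effects on repeated study outcomes". It lists no model terms.

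Aim 3 applies GEE Poisson models "for the four monthly ACASI assessments on numbers of sex partners" and three further behavioural counts. The list ends "condomless sex events with serodiscordant partners, including the baseline value". The stated MDEs at 80% power are reductions of 32% (male anal sex partners), 59% (serodiscordant condomless partners), 48% (condomless partners while intoxicated) and 58% (condomless events with serodiscordant partners). The inputs are attributed to a prior trial, without numbers.

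On timing, Section 1.4 says "the audio computer assisted survey instrument (ACASI) will be completed monthly", and Section 1.4.g says "The monthly visits (M1, M2 and M3) include safety labs". Table 3 schedules the sexual behaviour outcomes at enrolment, monthly, daily (texts) and post-treatment. Its key separates these codes: "Notes: E=Enrollment; M=Monthly; W=Weekly; D=Daily PT=Post-Treatment".

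Aim 1 says only "Baseline TLFB results will be included in the analysis". Table 3 schedules urine EtG at enrolment as well as during treatment, but the Aim 2 model does not mention a baseline result.

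**The concern.** Treatment cannot act on the enrolment survey. If that survey is a response record, the treatment effect is undiluted only when it is defined as a post-baseline contrast, and Aim 3 names none. An analyst could follow the text and fit one arm term over four records, which averages a record with no effect into three that have one. The estimate would move toward the null, power would fall, and any chance imbalance at baseline would enter the treatment estimate instead of being removed.

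Aim 3 is listed among the primary objectives in Section 1.2. The models that the wording permits range from one that loses about a quarter of the effect to one that has more power than the follow-ups alone. If the choice is left until the data are seen, it can also be made on the results.

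**Working it through.** **1. Which four assessments?** Three monthly surveys (M1, M2, M3) plus enrolment (E) make exactly four, and "including the baseline value" accounts for the fourth. M1-M3 plus the 1-month post-treatment survey also makes four, but leaves out the 3-month post-treatment survey without explanation. Section 1.4 reserves both post-treatment visits for durability. E+M1+M2+M3 is the more natural reading, though not the only one.

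**2. The plan's own figures.** The four count MDEs cannot be reproduced, because control means, over-dispersion, within-subject correlation and number of records are not given. The STI MDE can be checked approximately. With 120 randomised 1:1 and 80% retained, n = 60 x 0.80 = 48 per arm. At two-sided 5%, 80% power and control rates of 30-40%, the detectable difference is 22.2-25.2 points (pooled variance) or 24.3-26.4 points (log-odds). The stated 23-26 points fits that spread, so sample size, retention and alpha are consistent with the text.

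**3. Standard error implied by each count MDE.** SE = |ln(1 - reduction)| / (1.960 + 0.842). Two-sided 5% is assumed for these outcomes, because the text states it only for the STI figure. For this step, take the MDEs to refer to the three follow-ups.

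**4. Conditional dilution.** With one arm term over E, M1, M2 and M3, and a control mean assumed equal at all four surveys, the apparent rate ratio is (1 + 3 x true rate ratio)/4. For 32%: (1 + 3 x 0.68)/4 = 0.76, a 24% reduction.

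**5. Conditional power.** The Poisson GEE tests the log rate ratio, so the signal shrinks by ln(0.76)/ln(0.68) = 0.71 for the first outcome. Four exchangeable records instead of three change the SE by the factor √{[(1+3r)/4] / [(1+2r)/3]}. Example, 32% outcome at r = 0.3: the factor is √(0.475/0.533) = 0.944, the SE is 0.1377 x 0.944 = 0.130, and 0.274/0.130 - 1.96 = 0.15, which gives 56%.

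| True reduction | Implied SE | Diluted reduction | Power at r = 0.1 | r = 0.3 | r = 0.7 |
|---|---|---|---|---|---|
| 32% | 0.138 | 24.0% | 60% | 56% | 53% |
| 59% | 0.318 | 44.3% | 53% | 49% | 46% |
| 48% | 0.233 | 36.0% | 56% | 53% | 49% |
| 58% | 0.310 | 43.5% | 53% | 50% | 47% |

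The plan gives correlations of 0.1-0.3, for STIs only. Using any value for the counts is an assumption.

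**6. Simulation.** GEE Poisson, 48 per arm, true rate ratio 0.68, two illustrative variance settings (assumed):

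| Model | Estimated rate ratio | Power |
|---|---|---|
| Arm term over four records | 0.77-0.78 | 36-54% |
| Three follow-ups, no baseline | 0.68 | 62-78% |
| Baseline as record, arm-by-post-baseline term | 0.68 | 74-89% |
| Baseline as covariate | 0.68 | 75-88% |

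**7. Gain from a baseline covariate.** By a linear approximation, the variance goes from (1+2r)/3 to (1+2r)/3 - r². At r = 0.1 that is 0.400 to 0.390, and 80% power becomes 81%. At r = 0.3 it is 0.533 to 0.443, and 80% becomes 87%. The gain grows at higher assumed correlations.

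**8. Aim 1.** With one baseline week and twelve follow-up weeks (assumed), 1 - (1 + 12 x 0.72)/13 = 25.8%, so the stated 28% would become about 26%.

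**The case against.** A reader might infer that Aim 3 specifies a single arm term and therefore will dilute the effect. The text does not support that, because it names no terms at all. Listing baseline among the repeated records is normal for an arm-by-time or baseline-constrained model, and "including the baseline value" can also mean covariate adjustment; none of these dilutes. Some wording leans toward a change contrast: the Aim 1 models are meant to assess reductions, and the Aim 3 STI model compares arms over time. Against this, Section 1.7 spells out an interaction for the as-treated analysis and adjustment for baseline correlates of missingness, and Aim 3 has no such wording. The silence stands as a gap, not as a commitment to the diluting model.

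A reader might also infer that the stated MDEs are wrong or that the trial has less than 80% power. That cannot be shown, since the contrast, number of records and correlation behind the MDEs are not given.

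Two further points stand. The choice between a baseline covariate and an arm-by-post-baseline test is largely preference, since step 6 shows nearly equal performance. The point is also weak for the other aims: Aim 1 dilution would be small, and in Aim 2 the issue is unused baseline information rather than dilution.

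**Conclusion.** The point holds as a gap in specification with a conditional cost. The most natural reading makes enrolment one of four Aim 3 outcome records, and no post-baseline contrast is named. If one arm term over those records were the treatment effect, about a quarter of each reduction would be lost, and power would be about 46-60% instead of 80%. That power range rests on exchangeable correlation of 0.1-0.7, on a stable control mean, and on MDEs that refer to the three follow-ups; all three are assumptions. Under either standard alternative there is no dilution, and power exceeds that of the follow-ups alone. The plan should settle the matter before the data are seen.

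**What to change.** - **Aim 3:** state that the outcomes are the month 1, 2 and 3 ACASI assessments, that the participant's baseline value is a covariate (for example log(baseline + 1), which allows zeros), and that the arm term is the treatment effect. Alternatively, keep baseline as a record, constrain the arms to be equal at baseline, and test arm-by-post-baseline. Say that the logistic fallback models take the same form.
- **Aim 1:** use the same form for weekly binge days.
- **Aim 2:** adjust for the enrolment EtG result.
- **Power:** state the MDEs for the chosen contrast, with the number of records and the correlation used.

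The cost is a few sentences in Section 1.7 and a rerun of the MDEs with the inputs the sponsor already holds. No new data are needed.

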This study's aim is to determine efficacy of an herbal intervention to reduce binge drinking, against a background of relatively brief counseling that would be feasible in a clinical setting with limited resources. Thus, we will adapt a manualized version of the MM brief counseling platform used in NIAAA's COMBINE study.^{150,151} In that trial, pharmacotherapy with MM showed the most significant reductions in heavy drinking days compared to 7 other treatment arms.¹⁵⁰ MM has been used in a targeted pharmacotherapy trial 98 and our team has

successfully used MM in AUD trials. MM is a low-intensity supportive program designed to increase problem recognition and enhance motivation to change maladaptive alcohol use patterns. Participants will receive individual 20 minute MM sessions weekly from trained staff supervised by a clinical psychologist.

1.1. Measures and Schedule of Data Collection Overview.

1.1.a. Medical Safety Measures.

Blood specimens will be collected for monthly safety lab assessments via venipuncture by clinicians or research associates with certified phlebotomy training. Since San Francisco is facing the COVID-19 outbreak, we will collect safety lab assessments at 6 and 12 weeks* rather than monthly until the shelter-in-place order is lifted. This is for the safety of our participants.

Table 3: Summary of Measures	Data Source	Schedule*
OUTCOME VARIABLES		
Alcohol behavioral outcomes ^{152,153}		
No. of binge drinking sessions; drinks per drinking day	TLFB ¹⁵⁴ ; SMS texts	W, D, PT
Alcohol urinary biomarker		
Urine-positivity for ethyl glucuronide (EtG) for recent alcohol use (past 3 days)	Urine Sample	E, W-6, PT
Sexually Transmitted Infections outcomes		
Incident syphilis, gonorrhea, Chlamydia, or HIV; site of infections (urethral, oral or rectal).	Biologic Samples	E, M-3, PT
Behavioral outcomes ^{152,153}		
No. of sex partners and condomless sex acts; Event-level data on alcohol and recent episodes of sex ¹⁵⁵ ; Partners on PrEP or with undetectable viral load	ACASI, S MS texts	E, M, D, PT
PrEP use and adherence / Anti-retroviral Therapy (ART) use and adherence	ACASI	E, M
Reported days / episodes of other substance use	ACASI	E, M
Alcohol treatment (outside study)	ACASI	E, M
Adherence outcomes		
Frequency and timing of pill taking	MEMs cap Dispensers	D
Self-reported adherence	ACASI; SMS texts	M; D
Safety outcomes		
Adverse events ¹⁵⁶	Self-report	E, M
Safety labs (e.g., liver enzyme levels, renal function) ¹⁵⁶	Serum Sample	E, M*

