***Aim 4:** To evaluate the tolerability and acceptability of targeted kudzu versus placebo*, as determined by adverse clinical event rates and medication adherence (via data from MEMs capmonitoring and self-report from EMA and TLFB), by study arm. While laboratory studies have demonstrated the tolerability and acceptability of daily kudzu, we will examine these outcomes in an outpatient setting for targeted (prn) dosing. Adverse clinical events (AEs) and other binary safety outcomes will be presented as percent of participants that experience the safety outcome by treatment arm. Binary adverse effect measures will be analyzed using exact methods, since they are expected to be uncommon. We will measure the acceptability of kudzu among participants by determining medication adherence via MEMs cap opening events, pill count and self-report. Adherence measures of interest will include percent of doses taken during reported drinking days, patterns of adherence and time to stopping medication. We will assess how these measures of adherence track with patterns of alcohol use and binge drinking as reported in TLFB. GEE logistic models will be used to estimate the proportions of kudzu participants taking medication during periods of reported alcohol use and binge drinking. Concordance of adherence measures based on MEMs cap and self-report measures will be examined using weighted Kappa and correlations.

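### The models for gonorrhea and Chlamydia by anatomical site have no rule for sparse cells, and one analysed site is missing from the measures table

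*Combined protocol and SAP*

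**What the plan says.** Section 1.7, Aim 3 sets the model: "We will use GEE logistic regression models to evaluate differences in incidence of STIs between kudzu and placebo arms over time". Incidence is then evaluated as a composite, by three types (syphilis, gonorrhea, Chlamydia) and, "for gonorrhea and Chlamydia, by site (i.e., urethral, oral, vaginal, or rectal"). Two organisms at four sites make eight site-level outcomes. They are not labelled descriptive, and nothing is said about an arm without events.

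The only rates and the only detectable difference in that section concern STI incidence overall: "reductions of 23-26 percentage points in the incidence of STIs at month 3", for control rates of 30-40% and within-subject correlations of 0.1 to 0.3.

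Two other places bear on this. For Aim 4 the same section says: "Binary adverse effect measures will be analyzed using exact methods, since they are expected to be uncommon". Table 3 (Summary of Measures) describes the STI outcome with "site of infections (urethral, oral or rectal"), so the vaginal site is absent. Testing is scheduled there at enrollment, month 3 and post-treatment.

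**The concern.** A logistic model has no finite odds ratio when one arm has no events. GEE software does not reliably stop at that point. It can return a very large negative coefficient with a modest robust standard error, and so a spuriously tiny p-value. With few infections spread over eight site-level outcomes, this is a practical risk. Aim 3 is listed among the primary objectives in section 1.2, so a site-specific artefact could be reported as a finding. The plan already accepts, for adverse effects, that uncommon binary outcomes need exact methods, but it does not carry this over to the site-level infections.

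The site lists raise a separate question. Women are eligible: section 1.4.d gives them their own binge threshold and names vaginal sex, and randomization is stratified by gender. A vaginal analysis needs vaginal specimens, and the table that summarises the measures does not list them.

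**Working it through.** **Inputs.** "120 participants will be randomized 1:1 to kudzu extract (2 grams) or placebo" (section 1.4), so 60 per arm. "we conservatively estimate that 80% of participants will be retained at 12 weeks" (section 1.7, Aim 1), so 60 x 0.8 = 48 per arm. Composite rates (Aim 3): 30% against 30 - 23 = 7%, and 40% against 40 - 26 = 14%.

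**The plan's own figure.** The plan claims "80% power in 2-sided tests with a type-I error rate of 5% to detect reductions of 23-26 percentage points". The two-proportion formula with pooled variance under the null is d x sqrt(n) = 1.96 x sqrt(2 x pbar x (1 - pbar)) + 0.842 x sqrt(p0(1 - p0) + p1(1 - p1)). With n = 48 it gives d = 22.1 points at a 30% control rate and 25.2 at 40%. With the variance inflated by 1.1 (my assumption on how a correlation of 0.1 enters), it gives 23.0 and 26.2. The composite figure is therefore sound to within about a point and is not in dispute.

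**Composite events at month 3.** 48 x 0.30 = 14.4 against 48 x 0.07 = 3.4; or 48 x 0.40 = 19.2 against 48 x 0.14 = 6.7.

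**Split into cells (assumption; the documents give no rate by type or site).** One infection per positive participant, spread evenly in one of two ways:
- nine cells: syphilis plus eight organism-site cells, share 1/9;
- three types, then four sites within type, share 1/12 per site cell and 1/3 per type.

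Expected events per site cell are 1.2 to 2.1 in controls and 0.28 to 0.75 on kudzu.

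**Chance that at least one arm is empty.** P = 1 - [1 - (1 - p0 x s)^48] x [1 - (1 - p1 x s)^48], where s is the share. Example for 30% against 7% with s = 1/9: the control arm is empty with probability 0.196 and the kudzu arm with 0.687, so P = 1 - 0.804 x 0.313 = 0.75. For the pooled columns the exponent is 144, that is, three follow-up visits (month 3 and two post-treatment), each at the month 3 rate with 48 per arm and treated as independent.

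| Rates | Site, s = 1/9, month 3 | Site, s = 1/12, month 3 | Site, s = 1/9, pooled | Site, s = 1/12, pooled | Type, s = 1/3, month 3 |
|---|---|---|---|---|---|
| 30% v 7% | 75% | 83% | 33% | 45% | 33% |
| 40% v 14% | 53% | 65% | 11% | 19% | 10% |
| 30% v 30% | 35% | 50% | 1.5% | 5% | 1% |
| 40% v 40% | 21% | 35% | 0.3% | 1.5% | 0.2% |

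With two infections per positive participant, the month 3 site figures under the target effect fall to 23-61%.

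**What an empty arm does.** A single-visit GEE logistic fit with robust standard errors to 0/48 against 2/48 returns a log odds ratio of about -21.4 with standard error 0.74, so z is about -29 and p < 1e-100. Fisher's two-sided p is 2 x C(48,2)/C(96,2) = 2 x 1128/4560 = 0.49.

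**What the site cells can show.** Against 0/48, Fisher needs 6/48 for p < 0.05 (5/48 gives 0.056; 6/48 gives 0.027). With s = 1/12 its power under the target effect is below 1% per site cell. With s = 1/3 it is 15-17% per type.

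**The case against.** The strongest reply is that the plan does not itself imply empty cells. It gives a composite rate, and every cell count above comes from an even split that I assumed. That stands. A reader might infer that the plan's own rates leave an arm empty in most cells; the documents do not support this. It holds for site cells at month 3 if the full target effect occurs with about one infection per positive participant. With no effect the figure is 21-50%, and a detectable difference is a power input, not a forecast.

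The model compares arms over time, so counting month 3 alone discards scheduled post-treatment tests. That also stands: pooling lowers the risk to 11-45% under the effect and 0.3-5% with none. These pooled figures are favourable to the plan, because they assume full month 3 yield and no further loss at each visit. Under the target effect, the risk that remains is not negligible.

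A reader might also infer that GEE should be dropped for the types. The numbers do not support that: a type has an empty arm in 10-33% of cases under the effect and in about 0-1% without.

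Finally, these are sub-analyses within the third aim of a pilot, and no power is claimed for them. That limits the consequences. It does not remove the risk that software reports a false result.

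**Conclusion.** The concern holds for the organism-by-site analyses. They are planned with a model that can break down when an arm is empty, and no fallback is stated. Under an even split over 9 to 12 cells with one infection per positive participant, the chance of an empty arm per site cell is 53-83% at month 3 under the target effect and 21-50% with none. Unequal splits, and the unstated share of women for the vaginal cells, would make some cells sparser and others fuller. That an empty arm can produce false significance does not depend on the split. The composite model is unaffected, and the type-level models need only a rule for the occasional empty arm.

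The mismatch in site lists is plain in the text and needs no assumption. One might infer that infections in women will be under-counted. That follows only if Table 3 governs sampling. It is a summary of measures that gives the source simply as biologic samples, and no section says that it fixes the specimens taken.

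**What to change.** In section 1.7, Aim 3:
- Keep GEE logistic regression for the composite, and for each STI type when both arms have events.
- For the organism-by-site outcomes, and for any type with an empty arm, report the number of participants with the infection by arm, with Fisher's test or an exact risk-difference interval. Count each participant once over follow-up so that post-treatment tests are kept.
- Label the site results descriptive.
- Make the site lists in Aim 3 and Table 3 agree, so that every analysed site is a collected one.

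The cost is a few sentences and one table entry, and exact methods are already planned under Aim 4. The drawbacks are that exact methods are conservative, counting each participant once gives up the timing of infection, and the site cells will have almost no power. That last limit comes from the small number of events, so counts are what these cells can support.
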